### **Participant recruitment for Aim 3 (UH3 Phase, 2019-2021).**

Based on preliminary data, burden of opioid-related illness, and familiarity with supportive local stakeholders, we selected La Crosse County, Marathon County, and Brown County as the implementation sites for this study. Eau Claire, Douglas, and Outagamie Counties will serve as the

nonintervention sites, where participants will receive services as usual. In the fall of 2019, 3 full-time Prevention Navigators were hired and trained to conduct the intervention. Participants in this phase of the study will be recruited into one of two groups, Prevention Navigation, or usual services. Beginning in year 3, SSP clients at the 6 selected Vivent Health sites will be notified about the study by prevention specialists or SSP staff if the client 1) tests for HCV or HIV at the SSP, 2) inquires about services that may be in the prevention home through casual conversation, 3) the client engages in naloxone training, 4) through posted materials of the availability of new resources for improving prevention services and linkages to treatment in the SSP and community offices, 5) recruit through flyers and posted materials in the SSP and local community resource offices, and public areas, 6) through Vivent Health Facebook advertisements, 7) through our study website listed on our flyers, and/or 8) through respondent-driven sampling (RDS). Upon the completion of the first two attended Prevention Navigation sessions,

participants will be given a referral coupon and asked to refer one eligible peers per coupon to participate in the study. Vivent Health will dispense coupons that have been prepared by UW research staff. SSP clients at the nonintervention sites will be recruited at the time the Vivent Health staff member assists them with regular exchange services. Nonintervention sites will aim to enroll about one participant every-other week.

[figure not shown]
[figure not shown]

Figure 5. Parallel crossover (wait-list control) and cross-site study design

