**Eligibility screening and enrollment at baseline.** Individuals will be eligible for enrollment if they are 18 years of age or older, have injected any drug to get high in the past 1 month, and reside in a rural community. All persons who access services at the northern Wisconsin SSPs will be considered rural community members, so long as they reside in the state of Wisconsin. County of residence and zipcode will be collected, stored in the participant file, and recorded in REDCap.

Among nonintervention sites, eligibility criteria will be the same as intervention sites, with the exception of allowing Minnesota residents to participate in the Douglas County office.

At intervention sites the PN will administer the screening questionnaire in person or over the phone with the client. If the PN is not available, the client may answer the screening questionnaire on their own and immediately validate their answers with the PN before eligibility is determined (not applicable if virtual). Eligibility requirements will not be listed or shared with the clients. The screening questionnaire has been uploaded as part of the application. If the PN is unavailable, Vivent Health SSP staff will also be research trained and able to administer the screening questionnaire in person or over the phone.

If clients are determined to be eligible, then the research staff will collect their name and date of birth, and assign them a study ID number. They will then provide detailed information about the intervention, study procedures, and the consent document.

If the client agrees to participate, they will be read a verbal consent script over the phone, by video conference, or in-person by the prevention navigator, SSP staff, or UW staff. They will be required to answer T/F questions regarding the consent before giving verbal consent. Participants will fill out a locator form at this time to help SSP staff contact the participant for follow up visits.

Rapid testing for HIV and hepatitis C will be conducted by Vivent Health SSP staff, using standard procedures determined by the agency that are independent of the research protocol. The data collection forms used by the SSP staff will be shared with the research team in order to retrieve specific data elements needed for the study. Study forms will be securely transmitted to researchers after each research assessment.

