The goal of the Client-Centered Prevention Home program is to increase the knowledge of people who inject drugs on navigating prevention and treatment services for HIV, HCV, and drug overdose. We describe measures for our study population in the Appendix. Key sources for measurement will come from the ACASI survey that will be adapted from the ROI Harmonized UG3 survey, surveillance data gathered from the state of Wisconsin, and Medicaid health utilization data.

**1.4. Study data collection sites.** The main community partner, Vivent Health, will serve as the data collection and study site. Vivent Health is a statewide organization that provides harm reduction services, including syringe services and confidential HIV and HCV testing. As shown in Figure 1, three sites will be used for the intervention of the study: Brown County (Green Bay), Marathon County (Wausau), and La Crosse County (City of La Crosse). The 3 other Vivent Health offices that participated in the UG3 study phase, including Outagamie County (Appleton), Eau Claire County (City of Eau Claire), and Douglas County (Superior), will serve as recruitment sites for control group participants during the UH3 phase, but will not provide the prevention navigation intervention.

**1.5. Study sample description and inclusion and exclusion criteria.** Leveraging relationships developed among Vivent Health clients and community partners during the UG3 phase, we will recruit participants using Vivent Health staff at all six counties. In order to be part of the study, participants must meet the following eligibility criteria: 1) clients must be at least 18 years old, 2) have injected drugs to get high in the past 30 days, and 3) reside in one of the participating communities in or around one of the six participating counties.

Exclusion criteria are: (1) not speaking English fluently, (2) residing outside or being unwilling or unable to travel for study visits at one of the participating communities.

**1.6. Sample size.** A total of 405 participants will be enrolled to evaluate the intervention (Figure 1). Study procedures will vary for participants based on enrollment into 2 study groups, as follows:

- (a) 270 participants enrolled at intervention sites, who will receive prevention navigation.
- (b) 135 participants enrolled across the 3 non-intervention sites, who will serve as a contemporaneous control group.

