**(C) A cohort-study design comparing longer term outcomes using external data sources**

To detect changes in so-called “hard” outcomes such as enrollment in insurance, HCV cure, hospitalization, and initiation of medication assisted treatment, we will access sources such as the Wisconsin Medicaid data for all enrolled participants for up to 2 years after enrollment. This strategy is enabled by the data sharing agreements and database resources created through our JCOIN Supplement award in 2018-19. Additional data sources include the Wisconsin Electronic Disease Surveillance System and the Wisconsin Immunization Registry.

**1.8. Consent documents.** When a client agrees to participate in the Client-Centered Prevention Home, he or she will be informed about the research aims of the project by the Prevention Navigator during the intake encounter, they will be asked to provide informed consent to participate, and authorize the research team to use their health information. The consent form will cover information on the protocol, risks, benefits, and protections for the participant. It will also note the existence of a Certificate of Confidentiality for the intervention. The consent document will remind participants that their participation is voluntary, and that their decision of not participating will not jeopardize their relationship with ARCW and UW-Madison. Consenting participants will verbally consent, and a copy of the consent form will be available to them upon request. Additional consent documents will be signed for rapid HIV and HCV testing as per procedures from the Wisconsin Department of Health Services.

**1.9 Collection of data for research/evaluation,** In order to evaluate the effectiveness of the Client-Centered Prevention Home, data will be collected using various tools throughout the UH3 phase. Interested participants will first be screened for the study by the Prevention Navigator or research staff by phone or in person, respectively. Once screened eligible, participants will be tested for HIV, HCV, and syphilis at baseline, 3-month, and 6-month follow up. Testing forms

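### Client-level outcomes from Wisconsin registries are likely to be captured less completely for Minnesota residents, who may enrol only at one control site

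*Combined protocol and SAP*

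**What the plan says.** Protocol section 4.0 (Aim 3 eligibility) treats users of the northern Wisconsin syringe programs as rural residents "so long as they reside in the state of Wisconsin". Non-intervention sites use the same criteria "with the exception of allowing Minnesota residents to participate in the Douglas County office". The Aim 3 recruitment text states that "Eau Claire, Douglas, and Outagamie Counties will serve as the" comparison sites, so Douglas belongs to the control arm. Residence is on file: "County of residence and zipcode will be collected, stored in the participant file, and recorded in REDCap".

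Appendix 1, section 1.7(C), lists the longer-term outcomes as "enrollment in insurance, HCV cure, hospitalization, and initiation of medication assisted treatment". To obtain them, "we will access sources such as the Wisconsin Medicaid data for all enrolled participants for up to 2 years after enrollment". It continues: "Additional data sources include the Wisconsin Electronic Disease Surveillance System and the Wisconsin Immunization Registry". Protocol section 5.4 adds Department of Corrections data and state laboratory HCV records. It also says that the programmers of the linked state file will look for matches to study participants and for a comparison group.

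Appendix 2 defines several Medicaid outcomes (visits for medication-assisted treatment, fills for opioid-treatment drugs, fills for HCV antivirals) from the start of either the intervention or the control period. Enrolled controls are therefore meant to be measured.

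Nothing in the protocol or appendices limits the linked analyses by state of residence. Nothing says whether a person without a linked record counts as a non-event, as missing, or as excluded.

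**The concern.** Minnesota residents can enter the study only as controls, and the linked outcomes come from Wisconsin systems. A Minnesota resident treated or insured in Minnesota may leave no trace in those systems. Ascertainment would then differ by arm through an eligibility rule and not through anything the intervention did.

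The exposure is greatest for Medicaid claims: treatment visits and fills, HCV treatment fills, immunisation visits, and insurance enrolment itself. It is partial for HCV cure taken from the state surveillance system. In an open, non-randomised comparison the arms already differ by county. An added difference in who can be observed cannot be separated from a treatment effect afterwards unless the analysis population is defined for it.

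**Working it through.** **Inputs from the documents.** Aim 3 plans 270 intervention and 135 control participants, the controls spread over three sites, with 80% power for 28% versus 42% (section 7.0; Appendix 1, section 1.6).

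**Assumptions.** The split by site is not stated; I take 135/3 = 45 at Douglas. The Minnesota share m of Douglas controls is not stated; I show 10% to 100%. Alpha for Aim 3 is not stated; I use two-sided 5%. Minnesota residents are taken to have no linked record, scored as no event.

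**The plan's power figure.** With a pooled two-proportion test:
- mean rate = (0.28 + 2 × 0.42)/3 = 0.373
- null SE = √[0.373 × 0.627 × (1/135 + 1/270)] = 0.0510
- alternative SE = √[0.28 × 0.72/135 + 0.42 × 0.58/270] = 0.0489
- z = (0.14 − 1.96 × 0.0510)/0.0489 = 0.82, so power is 79.4%

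This reproduces the stated 80%.

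**False difference in a level.** If the true rate is p in both arms, the observed control rate is p × (1 − 45m/135) = p(1 − m/3). The false difference is p × m/3.

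| m | Minnesota controls | p = 28%: control rate, false difference | Type I error | p = 10%: false difference | Type I error |
|---|---|---|---|---|---|
| 10% | 4.5 | 27.1%, 0.9 points | 5.4% | 0.3 points | 5.0% |
| 25% | 11.25 | 25.7%, 2.3 points | 7.6% | 0.8 points | 5.5% |
| 50% | 22.5 | 23.3%, 4.7 points | 16.6% | 1.7 points | 7.7% |
| 100% | 45 | 18.7%, 9.3 points | 53.7% | 3.3 points | 18.4% |

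The 28% is a survey planning rate used as a yardstick; the documents give no rates for the linked outcomes.

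**Direction.** Under-counting control events raises the apparent benefit when the event is favourable (treatment start, HCV treatment or cure, insurance, immunisation). For hospitalization it works the other way. Take an illustrative true fall from 28% in controls to 20% with the intervention, a difference of −8.0 points. The observed difference is 20% − 28% × (1 − m/3):
- m = 25%: −5.7 points
- m = 50%: −3.3 points
- m = 100%: +1.3 points

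**Change measures.** Appendix 2 expresses most Medicaid outcomes as change over time. A person invisible to the registry contributes zero before and zero after. If controls truly change by d, the observed control change is d(1− m/3) and the error is d × m/3. With d = 0 there is no error; with an illustrative d of 10 points it is 0.3 points at m = 10% and 1.7 at m = 50%.

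**The case against.** The strongest reply is that the bias is conditional and may be small. Four parts of it stand.

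- **Scoring.** Non-event scoring is assumed, because the plan is silent. If unlinked people were set to missing or excluded, this mechanism would not operate. The comparison group from the linked state file might also replace the enrolled controls; the plan does not say.
- **Coverage.** A reader might infer that Minnesota controls cannot show an event at all. The documents do not support that. Section 5.4 sends the program's own test results to the surveillance system and reactive samples to the state laboratory, so capture there is partial.
- **Scope.** The immunisation-registry rows and the overdose-hospitalization row in Appendix 2 are county-level, so enrolled Minnesota residents do not affect them through linkage. Client-level hospitalization is named only in section 1.7(C). The survey, the main Aim 3 data source, needs no linkage.
- **Size.** The 28% and 42% belong to a survey item on access to addiction treatment. Setting the false difference against the 14-point planning effect compares unlike outcomes, and nothing in the documents supports a 50% share over a 10% one.

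A reader might also infer that the error always favours the intervention. Hospitalization shows that it does not.

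None of this removes the asymmetry. The exception is written for one control site, which section 5.1 places near Duluth, and section 1.7(C) covers everyone enrolled. Event definitions such as any visit or any fill make a missing claim easy to read as a non-event.

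**Conclusion.** The concern holds in a limited form. As written, the plan is likely to produce less complete ascertainment for some controls and for no intervention participants. This applies to client-level outcomes from Wisconsin sources, chiefly Medicaid claims. If unlinked people are scored as no event, favourable outcomes are biased toward the intervention and client-level hospitalization against it.

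The size cannot be fixed from the documents. It is minor if few Douglas controls live in Minnesota and material for common events if half or more do. It rests on an equal split of controls across sites, on non-event scoring, and on the inference about Medicaid coverage. For change measures it depends on the true change in controls and not on the level.

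**What to change.** In Appendix 1, section 1.7(C), and the Aim 3 analysis text, redefine the population for every client-level outcome taken from a Wisconsin administrative source (Medicaid, disease surveillance, immunisation registry, Department of Corrections). In place of everyone enrolled, use participants in both arms who had a Wisconsin address at enrolment, identified from the recorded county and ZIP code. Keep Minnesota residents in the survey analyses. Residence at enrolment is a baseline variable, so the restriction does not condition on later insurance coverage, which navigation may itself change.

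The cost is one sentence and the loss of Minnesota controls from the linked comparisons. Controls become 135 − 45m. On the planning rates, with 270 intervention participants, power falls from 79.4% to:
- 78.4% at m = 10% (130.5 controls)
- 76.9% at m = 25% (123.75)
- 73.9% at m = 50% (112.5)
- 66.5% if every Douglas control lived in Minnesota (90)

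The restriction does not settle how Wisconsin residents without Medicaid are scored; that can affect both arms and needs its own rule. Separately, Appendix 1, section 1.5, asks only that participants "reside in one of the participating communities in or around one of the six participating counties" and names no state. It should be reconciled with section 4.0.

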## 5.0 DATA COLLECTION

### 5.1 Data collection for Aim 1.

**Epidemiologic survey and needs assessment for rural WI.** During years 1 and 2 of this project, we will conduct a cross-sectional prevalence study among residents of rural communities in the catchment areas surrounding 6 Vivent Health Prevention Offices (Figure 3). Four of these offices are located in counties (Eau Claire, La Crosse, Marathon, Outagamie) classified by the National Center for Health Statistics (NCHS) as rural. Douglas and Brown Counties are not classified as rural by virtue of their proximity to the larger cities of Duluth, MN and Green Bay, WI, respectively. Both counties have total populations of fewer than 250,000 residents, however, and our analysis of residential ZIP codes provided by SSP clients showed that the Vivent Health offices in these counties served clients from a large geographic area across rural Northern Wisconsin, where the prevalence of HCV among young people who inject drugs is highest.

**Rapid testing for infectious diseases.** Upon enrollment, participants will provide 3 fingerstick whole blood samples for rapid testing of HIV, HCV and syphilis. Vivent Health prevention staff are trained to perform point-of-care tests for these infections using the Alere Determine™ HIV-1/2 Ag/AB Combo (Alere Inc., Waltham, MA); the OraQuick® HCV Rapid Antibody Test (OraSure Technologies, Bethlehem, PA); and the Syphilis Health Check™ (Trinity Biotech, Bray, Co Wicklow, Ireland), respectively. During the 20 minutes while awaiting test results, participants will complete an interviewer-administered survey (described below). If all 3 rapid tests are non-reactive, then the study visit will end after he or she has completed the questionnaire and received recruitment training and referral coupons. If any of the 3 rapid tests are reactive, then SSP staff will perform venipuncture to collect a blood specimen to be sent to the Wisconsin State Laboratory of Hygiene (WSLH) for confirmatory testing, record multiple methods of re-contacting the client, and arrange a follow-up visit to review confirmatory test results and provide linkage to care, if needed. In the event that a participant cannot provide a blood specimen for confirmatory testing due to poor venous access, they will be invited to return at a later date for another blood draw attempt. Those confirmed to have active HIV, HCV, or syphilis infection will be linked to a local provider with the assistance of a Vivent Health case manager.

**Laboratory-based confirmatory testing and specimen handling.** Specimens received by WSLH will be processed for confirmatory testing per standard protocols (see Facilities and Resources for details). After completing the required testing and reporting test results to the testing agency and the WI Surveillance System, WSLH staff will store plasma specimens in preparation for shipping to the CDC and/or GHOST laboratories, as described in Section 5.2

**Collection of baseline demographic and risk behavior data.** We worked closely with the Vivent Health Director of Prevention and syringe program staff to develop strategies to ensure that research activities are minimally-disruptive to the daily, core prevention activities of ARCW staff. Our pilot studies within SSPs have shown that this is essential for ensuring study protocol fidelity, maintaining high-quality data collection, and maximizing client willingness to participate. We will take advantage of existing data collection forms that are used during HIV and HCV testing encounters to capture necessary individual-level data elements. All publicly-funded HIV testing sites in WI are required to use a uniform data collection and reporting system called Evaluation Web (Luther Consulting, LLC, Carmel, IN). Rapid HCV testing supported by WI DHS requires that agencies report client-level data

using the Wisconsin Electronic Disease Surveillance System (WEDSS). With participant consent, the paper data collection forms used to capture the required demographic and risk behavior information will be transmitted to the UW-Madison based study coordinator via secure fax-to-PDF system, and will be stored on an encrypted server in a directory separate from other study data.

Additionally, the laboratory infrastructure upon which the Wisconsin UG3 study was developed allows an opportunity to undertake a broader epidemiologic investigation that will more fully characterize the HCV epidemic in rural Wisconsin. All blood samples collected for HCV RNA confirmatory testing in the state of Wisconsin undergo testing at the Wisconsin State Laboratory of Hygiene (WSLH). The WSLH retains serum specimens from positive and negative confirmatory HCV RNA tests for up to 5 years. Using stored serum specimens collected during 2016-2017, we will conduct a baseline investigation of transmission clusters involving residents of rural Wisconsin communities.

**Baseline Survey.** Data elements not captured through existing workflows of SSP staff but necessary to achieve the research aims will be collected using a research team administered phone survey. At least two staff member will be available at all times during business hours. We will have 3 researchers available most days and develop an “on call” system to facilitate 2 phone-based study assessments by phone at a time. The survey will consist of short answer and multiple choice questions designed to efficiently assess drug use history, access and utilization of prevention services, and injection related risk behaviors (see **Appendix 2** for proposed measures).

To maximize willingness of clients to participate within the context of a routine Vivent Health prevention encounter, we will pilot-test the survey to ensure it can be completed within 20-25 minutes.

To facilitate recruitment of participants who have difficulty traveling to Vivent Health offices, we will begin recruiting and enrolling participants at outreach events that are organized by Vivent Health. We described the steps for recruitment and enrollment above. The survey will be administered during the outreach event via computer if there is an adequate internet connection. To increase flexibility in these settings, the survey may also be conducted via telephone with a UW-Madison researcher, who will administer the questionnaire verbally and enter responses directly into the Qualtrics survey. If internet or phone communication is not feasible, then a research assistant may administer the questionnaire in person using a pen-and-paper version. In this situation, the research assistant will subsequently perform data entry.

A data use agreement has been set forth between the University of Wisconsin-Madison and University of Washington, where a limited dataset from the University of Wisconsin is required to be submitted to the University of Washington as part of the NIH-funded Rural Opioid Initiative data harmonization project. The University of Washington Data Harmonization Coordinating Center (DCC) will be harmonizing data across eight sites in order to create new, combined datasets to be used for analyses across the consortium. Only data from this study (#2017-0866) will be sent to the DCC from UW-Madison.

Harmonization means the DCC will be combining similar data domains and questions across all sites in order to build large data sets that will be useful in answering questions that individual sites are not able to answer alone, either due to the nature of the question or sample size limitations. The University of Washington and other grantees will perform data analyses on these data for peer-reviewed publication. The harmonized datasets will be provided to other investigators funded under this study as required for analysis and will be considered under the umbrella of mandated DCC activities.

Upon execution of the agreement, the team’s data manager will upload study datasets to the Rural Opioid Initiative (ROI) Upload Server through a web interface. Access to the interface is controlled by usernames and passwords. Access is assigned to individual, designated ROI staff by the University

of Washington Data Coordinating Center (DCC). The web page uses the HTTPS protocol to transfer ROI data files securely to the Upload Server. HTTPS transfers are encrypted using Transport Layer Security (TLS, the successor to SSL), protecting the data en route to the server. The Upload Server is managed in accordance with the DCC's information security policies (<https://uwcirc.github.io/hipaa-policies>), and authorization for specific DCC staff is based on their project-related needs and responsibilities.

Data documentation will also be uploaded in the form of a data dictionary specifying all data elements within the dataset, including their description, valid values, and data type. Upon receipt of the dataset and documentation, the DCC data manager will work with the Wisconsin ROI data manager to understand the data structures so that the DCC may harmonize the dataset with those from other sites. A list of data elements that will be sent to the DCC is included in Appendix 3.

Table 6. Quantitative measures collected for Aim 1

Variable	Source	Measure/Operational Definition
Prevalence of HIV, HCV, , syphilis	Point-of-care screening + laboratory confirmation	Number of confirmed active cases / total number screened
Access to 9 prevention services	Participant questionnaire	Perceived accessibility using 5-pt Likert scales
Health insurance	Participant questionnaire	Access to Care Scale†59
Addiction severity	Participant questionnaire	Severity of Dependence Scale60
Barriers to care	Participant questionnaire	Kalichman's Barriers to Care Scale†61
HIV/HCV/STI risk behaviors	HIV/HCV Testing Data Collection Forms	NHME Data Variable Set‡
Demographic characteristics	HIV/HCV Testing Data Collection Forms	NHME Data Variable Set‡

† NIDA STTR Data Harmonization Measure; ‡ NHME=National HIV Prevention Program Monitoring and Evaluation

